8. ADVERSE EVENT REPORTING

8.1. Adverse Events

All observed or volunteered AEs regardless of treatment group or suspected causal relationship to the investigational product(s) will be reported as described in the following sections.

For all AEs, the investigator must pursue and obtain information adequate both to determine the outcome of the AE and to assess whether it meets the criteria for classification as an serious adverse event (SAE) requiring immediate notification to Pfizer or its designated representative. For all AEs, sufficient information should be obtained by the investigator to determine the causality of the AE. The investigator is required to assess causality.

Follow-up by the investigator may be required until the event or its sequelae resolve or stabilize at a level acceptable to the investigator, and Pfizer concurs with that assessment.

As part of ongoing safety reviews conducted by the sponsor, any nonserious AE that is determined by the sponsor to be serious will be reported by the sponsor as an SAE. To assist in the determination of case seriousness, further information may be requested from the investigator to provide clarity and understanding of the event in the context of the clinical study.

8.2. Reporting Period

For SAEs, the active reporting period to Pfizer or its designated representative begins from the time that the subject provides informed consent, which is obtained prior to the subject's participation in the study, ie, prior to undergoing any study-related procedure and/or receiving investigational product, through and including 28 calendar days after the last administration of the investigational product. SAEs occurring to a subject after the active reporting period has ended should be reported to the sponsor if the investigator becomes aware of them; at a minimum, all SAEs that the investigator believes have at least a reasonable possibility of being related to study drug are to be reported to the sponsor.

AEs (serious and nonserious) should be recorded on the Case Report Form (CRF) from the time the subject has taken at least 1 dose of study treatment through the last subject visit.

8.3. Definition of an Adverse Event

An AE is any untoward medical occurrence in a clinical investigation subject administered a product or medical device; the event need not necessarily have a causal relationship with the treatment or usage. Examples of AEs include but are not limited to:

- Abnormal test findings;
- Clinically significant symptoms and signs:
- Changes in physical examination findings;
- Hypersensitivity;
- Progression/worsening of underlying disease
- Drug abuse;
- Drug dependency.

Additionally, they may include the signs or symptoms resulting from:

- Drug overdose;
- Drug withdrawal;

- Drug misuse;
- Drug interactions;
- Extravasation;
- Exposure during pregnancy (EDP);
- Exposure via breastfeeding;
- Medication error;
- Occupational exposure.

8.4. Medication Errors

Medication errors may result, in this study, from the administration or consumption of the wrong drug, by the wrong subject, at the wrong time, or at the wrong dosage strength (eg, wrong number of tablets). Such medication errors occurring to a study participant are to be captured on the medication error case report form (CRF) which is a specific version of the adverse event (AE) page, and on the SAE form when appropriate. In the event of medication dosing error, the sponsor should be notified immediately.

Medication errors are reportable irrespective of the presence of an associated AE/SAE, including:

- Medication errors involving subject exposure to the investigational product;
- Potential medication errors or uses outside of what is foreseen in the protocol that do or do not involve the participating subject.

Whether or not the medication error is accompanied by an AE, as determined by the investigator, the medication error should be captured on the medication error version of the adverse event (AE) page and, if applicable, any associated AE(s) are captured on an AE CRF page.

8.5. Abnormal Test Findings

The criteria for determining whether an abnormal objective test finding should be reported as an AE are as follows:

- Test result is associated with accompanying symptoms; and/or
- Test result requires additional diagnostic testing or medical/surgical intervention; and/or
- Test result leads to a change in study dosing or discontinuation from the study, significant additional concomitant drug treatment, or other therapy; and/or

• Test result is considered to be an AE by the investigator or sponsor.

Merely repeating an abnormal test, in the absence of any of the above conditions, does not constitute an AE. Any abnormal test result that is determined to be an error does not require reporting as an AE.

8.6. Serious Adverse Events

An SAE is any untoward medical occurrence at any dose that:

- Results in death;
- Is life-threatening (immediate risk of death);
- Requires inpatient hospitalization or prolongation of existing hospitalization;
- Results in persistent or significant disability/incapacity (substantial disruption of the ability to conduct normal life functions);
- Results in congenital anomaly/birth defect.

Medical and scientific judgment is exercised in determining whether an event is an important medical event. An important medical event may not be immediately life-threatening and/or result in death or hospitalization. However, if it is determined that the event may jeopardize the subject or may require intervention to prevent one of the other AE outcomes, the important medical event should be reported as serious.

Examples of such events are intensive treatment in an emergency room or at home for allergic bronchospasm; blood dyscrasias or convulsions that do not result in hospitalization; or development of drug dependency or drug abuse.

8.6.1. Protocol-Specified Serious Adverse Events

There are no protocol-specified SAEs in this study. All SAEs will be reported by the investigator as described in previous sections, and will be handled as SAEs in the safety database (see section on Serious Adverse Event Reporting Requirements).

8.6.2. Potential Cases of Drug-Induced Liver Injury

Abnormal values in aspartate transaminase (AST) and/or alanine transaminase (ALT) levels concurrent with abnormal elevations in total bilirubin level that meet the criteria outlined below in the absence of other causes of liver injury are considered potential cases of drug-induced liver injury (potential Hy's law cases)⁷⁷ and should always be considered important medical events.

The threshold of laboratory abnormalities for a potential case of drug-induced liver injury depends on the subject's individual baseline values and underlying conditions. Subjects who

present with the following laboratory abnormalities should be evaluated further to definitively determine the etiology of the abnormal laboratory values:

- Subjects with AST or ALT and total bilirubin baseline values within the normal range who subsequently present with AST or ALT values ≥3 times the upper limit of normal (X ULN) concurrent with a total bilirubin value ≥2 X ULN with no evidence of hemolysis and an alkaline phosphatase value ≤2 X ULN or not available;
- For subjects with preexisting ALT **OR** AST **OR** total bilirubin values above the ULN, the following threshold values should be used in the definition mentioned above:
 - For subjects with preexisting AST or ALT baseline values above the normal range: AST or ALT values ≥2 times the baseline values and ≥3 X ULN, or ≥8 X ULN (whichever is smaller).

Concurrent with

• For subjects with preexisting values of total bilirubin above the normal range: Total bilirubin level increased from baseline by an amount of at least 1 X ULN or if the value reaches ≥3 X ULN (whichever is smaller).

The subject should return to the investigational site and be evaluated as soon as possible, preferably within 48 hours from awareness of the abnormal results. This evaluation should include laboratory tests, detailed history, and physical assessment.

In addition to repeating measurements of AST and ALT, laboratory tests should include albumin, creatine kinase, total bilirubin, direct and indirect bilirubin, gamma-glutamyl transferase, prothrombin time (PT)/international normalized ratio (INR), and alkaline phosphatase. A detailed history, including relevant information, such as review of ethanol, acetaminophen, recreational drug and supplement consumption, family history, occupational exposure, sexual history, travel history, history of contact with a jaundiced person, surgery, blood transfusion, history of liver or allergic disease, and work exposure, should be collected. Further testing for acute hepatitis A, B, or C infection and liver imaging (eg, biliary tract) may be warranted. All cases confirmed on repeat testing as meeting the laboratory criteria defined above, with no other cause for liver function test (LFT) abnormalities identified at the time, should be considered potential Hy's law cases⁷⁷ irrespective of availability of all the results of the investigations performed to determine etiology of the abnormal LFTs. Such potential Hy's law cases should be reported as SAEs.

8.7. Hospitalization

Hospitalization is defined as any initial admission (even less than 24 hours) in a hospital or equivalent healthcare facility or any prolongation to an existing admission. Admission also includes transfer within the hospital to an acute/intensive care unit (eg, from the psychiatric wing to a medical floor, medical floor to a coronary care unit, or neurological floor to a

tuberculosis unit). An emergency room visit does not necessarily constitute a hospitalization; however, the event leading to the emergency room visit should be assessed for medical importance.

Hospitalization does not include the following:

- Rehabilitation facilities;
- Hospice facilities;
- Respite care (eg, caregiver relief);
- Skilled nursing facilities;
- Nursing homes;
- Same-day surgeries (as outpatient/same-day/ambulatory procedures).

Hospitalization or prolongation of hospitalization in the absence of a precipitating, clinical AE is not in itself an SAE. Examples include:

- Admission for treatment of a preexisting condition not associated with the development of a new AE or with a worsening of the preexisting condition (eg, for workup of persistent pre-treatment laboratory abnormality);
- Social admission (eg., subject has no place to sleep);
- Administrative admission (eg, for yearly physical examination);
- Protocol-specified admission during a study (eg, for a procedure required by the study protocol);
- Optional admission not associated with a precipitating clinical AE (eg, for elective cosmetic surgery);
- Hospitalization for observation without a medical AE;
- Preplanned treatments or surgical procedures. These should be noted in the baseline documentation for the entire protocol and/or for the individual subject;

Diagnostic and therapeutic noninvasive and invasive procedures, such as surgery, should not be reported as AEs. However, the medical condition for which the procedure was performed should be reported if it meets the definition of an AE. For example, an acute appendicitis that begins during the AE reporting period should be reported as the AE, and the resulting appendectomy should be recorded as treatment of the AE.

8.8. Severity Assessment

If required on the AE CRFs, the investigator will use the adjectives MILD, MODERATE, or SEVERE to describe the maximum intensity of the AE. For purposes of consistency, these intensity grades are defined as follows:

MILD	Does not interfere with subject's usual function.
MODERATE	Interferes to some extent with subject's usual function.
SEVERE	Interferes significantly with subject's usual function.

Note the distinction between the severity and the seriousness of an AE. A severe event is not necessarily an SAE. For example, a headache may be severe (interferes significantly with the subject's usual function) but would not be classified as serious unless it met one of the criteria for SAEs, listed above.

8.9. Causality Assessment

The investigator's assessment of causality must be provided for all AEs (serious and nonserious); the investigator must record the causal relationship in the CRF, as appropriate, and report such an assessment in accordance with the SAE reporting requirements if applicable. An investigator's causality assessment is the determination of whether there exists a reasonable possibility that the investigational product caused or contributed to an AE; generally the facts (evidence) or arguments to suggest a causal relationship should be provided. If the investigator does not know whether or not the investigational product caused the event, then the event will be handled as "related to investigational product" for reporting purposes, as defined by the sponsor (see section on Reporting Requirements). If the investigator's causality assessment is "unknown but not related to investigational product," this should be clearly documented on study records.

In addition, if the investigator determines that an SAE is associated with study procedures, the investigator must record this causal relationship in the source documents and CRF, as appropriate, and report such an assessment in accordance with the SAE reporting requirements, if applicable.

8.10. Exposure During Pregnancy

For investigational products and for marketed products, an exposure during pregnancy occurs if:

1. A female becomes, or is found to be, pregnant either while receiving or having been exposed (eg, because of treatment or environmental exposure) to the investigational product; or the female becomes, or is found to be pregnant after discontinuing and/or being exposed to the investigational product;

An example of environmental exposure would be a case involving direct contact with a Pfizer product in a pregnant woman (eg, a nurse reports that she is pregnant and has been exposed to chemotherapeutic products).

2. A male subject has been exposed (eg, because of treatment or environmental exposure) to the investigational product prior to or around the time of conception and/or is exposed during his partner's pregnancy.

If a study subject or study subject's partner becomes or is found to be pregnant during the study subject's treatment with the investigational product, the investigator must submit this information to the Pfizer drug safety unit on a Serious Adverse Event (SAE) Report Form and Exposure During Pregnancy (EDP) supplemental form, regardless of whether an SAE has occurred. In addition, the investigator must submit information regarding environmental exposure to a Pfizer product in a pregnant woman (eg, a subject reports that she is pregnant and has been exposed to a cytotoxic product by inhalation or spillage) using the EDP supplemental form. This must be done irrespective of whether an AE has occurred and within 24 hours of awareness of the exposure. The information submitted should include the anticipated date of delivery (see below for information related to termination of pregnancy).

Follow-up is conducted to obtain general information on the pregnancy and its outcome for all EDP reports with an unknown outcome. The investigator will follow the pregnancy until completion or until pregnancy termination) and notify Pfizer of the outcome as a follow-up to the initial EDP supplemental form. In the case of a live birth, the structural integrity of the neonate can be assessed at the time of birth. In the event of a termination, the reason(s) for termination should be specified and, if clinically possible, the structural integrity of the terminated fetus should be assessed by gross visual inspection (unless preprocedure test findings are conclusive for a congenital anomaly and the findings are reported).

If the outcome of the pregnancy meets the criteria for an SAE (ie, ectopic pregnancy, spontaneous abortion, intrauterine fetal demise, neonatal death, or congenital anomaly [in a live born, a terminated fetus, an intrauterine fetal demise, or a neonatal death]), the investigator should follow the procedures for reporting SAEs.

Additional information about pregnancy outcomes that are reported as SAEs follows:

- Spontaneous abortion includes miscarriage and missed abortion;
- Neonatal deaths that occur within 1 month of birth should be reported, without regard to causality, as SAEs. In addition, infant deaths after 1 month should be reported as SAEs when the investigator assesses the infant death as related or possibly related to exposure to investigational product.

Additional information regarding the exposure during pregnancy may be requested by the investigator. Further follow-up of birth outcomes will be handled on a case-by-case basis (eg, follow-up on preterm infants to identify developmental delays). In the case of paternal exposure, the investigator will provide the study subject with the Pregnant Partner Release of

Information Form to deliver to his partner. The investigator must document in the source documents that the subject was given the Pregnant Partner Release of Information Form to provide to his partner.

8.11. Occupational Exposure

An occupational exposure occurs when during the performance of job duties, a person (whether a healthcare professional or otherwise) gets in unplanned direct contact with the product, which may or may not lead to the occurrence of an adverse event.

An occupational exposure is reported to safety within 24 hours of Investigator's awareness, using the SAE Report form, regardless of whether there is an associated AE/SAE. Since the information does not pertain to a subject enrolled in the study, the information is not reported on a Case Report Form (CRF), however a copy of the completed SAE Report form is maintained in the study master file.

8.12. Withdrawal Due to Adverse Events (See Also Section on Subject Withdrawal)

Withdrawal due to AE should be distinguished from withdrawal due to other causes, according to the definition of AE noted earlier, and recorded on the appropriate AE CRF page.

When a subject withdraws because of an SAE, the SAE must be reported in accordance with the reporting requirements defined below.

8.13. Eliciting Adverse Event Information

The investigator is to report all directly observed AEs and all AEs spontaneously reported by the study subject. In addition, each study subject will be questioned about AEs.

8.14. Reporting Requirements

Each AE is to be assessed to determine if it meets the criteria for SAEs. If an SAE occurs, expedited reporting will follow local and international regulations, as appropriate.

8.14.1. Serious Adverse Event Reporting Requirements

If an SAE occurs, Pfizer is to be notified within 24 hours of investigator awareness of the event

In particular, if the SAE is fatal or life-threatening, notification to Pfizer must be made immediately, irrespective of the extent of available AE information. This time frame also applies to additional new information (follow-up) on previously forwarded SAE reports as well as to the initial and follow-up reporting of exposure during pregnancy, exposure via breastfeeding and occupational exposure cases.

In the rare event that the investigator does not become aware of the occurrence of an SAE immediately (eg, if an outpatient study subject initially seeks treatment elsewhere), the

investigator is to report the event within 24 hours after learning of it and document the time of his or her first awareness of the AE.

For all SAEs, the investigator is obligated to pursue and provide information to Pfizer in accordance with the time frames for reporting specified above. In addition, an investigator may be requested by Pfizer to obtain specific additional follow-up information in an expedited fashion. This information collected for SAEs is more detailed than that captured on the AE CRF. In general, this will include a description of the AE in sufficient detail to allow for a complete medical assessment of the case and independent determination of possible causality. Information on other possible causes of the event, such as concomitant medications, vaccines, and/or illnesses, must be provided. In the case of a subject death, a summary of available autopsy findings must be submitted as soon as possible to Pfizer or its designated representative.

8.14.2. Nonserious Adverse Event Reporting Requirements

All AEs will be reported on the AE page(s) of the CRF. It should be noted that the form for collection of SAE information is not the same as the AE CRF. Where the same data are collected, the forms must be completed in a consistent manner. For example, the same AE term should be used on both forms. AEs should be reported using concise medical terminology on the CRFs as well as on the form for collection of SAE information.

8.14.3. Sponsor Reporting Requirements to Regulatory Authorities

AE reporting, including suspected unexpected serious adverse reactions, will be carried out in accordance with applicable local regulations.

9. DATA ANALYSIS/STATISTICAL METHODS

Detailed methodology for summary and statistical analyses of the data collected in this study will be documented in a statistical analysis plan (SAP), which will be maintained by the sponsor. This document may modify the plans outlined in the protocol; however, any major modifications of the primary endpoint definition and/or its analysis will also be reflected in a protocol amendment.

9.1. Sample Size Determination

This is an open-label extension study. Subjects who complete the A8241021 study and are deemed eligible for this study per inclusion/exclusion criteria will be given the opportunity to enroll in this open label study. It is estimated that up to 260 subjects may participate in this extension study.

9.2. Efficacy Analysis

All endpoints will be evaluated over the Full Analysis Set (FAS), which is the set of subjects who have an extension study baseline efficacy evaluation, took ≥1 dose of open-label study medication. Subjects without post-dose measurements will not contribute to the analysis, except in the description of the baseline values.

9.2.1. Analysis of Primary Endpoint

The primary trial variables examine long-term safety and tolerability of therapy with 20 mg BID of PF-02545920. The primary analysis of long-term safety will be focused on Adverse events, weight, vital signs (pulse, blood pressure and body temperature), physical examination, neurological examination, electrocardiogram (ECG) and clinical laboratory findings (hematology, biochemistry and urinalysis).

The endpoints are:

- The number and proportion of subjects with adverse events.
- Assessment of clinical laboratory parameters.
- Assessment of vital signs.
- Assessment of ECG parameters.
- White blood count (WBC) and absolute neutrophil count (ANC) at each visit.
- Abnormal laboratory findings from baseline.
- Frequency and severity of adverse events related to extrapyramidal symptoms (EPS) including dystonia and akathisia, as assessed by the investigator.
- C-SSRS (suicide severity assessment).

Adverse events will be coded for analysis with MedDRA[®], and the number and percent of subjects reporting each event will be summarized. Descriptive statistics will be displayed to provide an overview of the safety results. For categorical parameters, these consist of the number and percent of subjects in each category. The denominator for percentages will be based on the number of subjects appropriate for the purpose of analysis. For continuous parameters, descriptive statistics includes n, mean, standard deviation (SD), median, minimum, and maximum. Subjects who prematurely discontinued the trial will be evaluated on the basis of data collected at each visit attended.

Safety analyses will be performed on the safety population, which includes all subjects who received at least 1 dose of study medication during the open-label period.

Further information about the safety analysis can be found in Section 9.5.

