3. STUDY DESIGN

This study is a 12 month open label extension study of PF-02545920 20 mg dosed BID following study A8241021.

The study includes a Screening visit (V1) to assess eligibility followed by a Baseline visit (V2) and visits after 2 weeks, 4 weeks, 3 months, 6 months, 9 months, and 12 months of treatment. The final scheduled visit is a Follow-up visit 7-14 days after the last dose. Screening visit (V1) and Baseline visit (V2) will coincide with Week 19 and Week 26 Visits from study A8241021, respectively. For the Screening visit (V1) and Baseline visit (V2) procedures and assessments, the investigator will use data collected during Week 19 and Week 26 visits for study A8241021, respectively. Subjects, who meet study entry criteria, will be assigned to the 20 mg BID dose. During the 12-month treatment phase, subjects will return for study assessments at Week 2 (V3), Week 4 (V4), Month 3 (V5), Month 6 (V6), Month 9 (V7), Month 12 (V8), and for a Follow-up visit (V9).

Subjects, who were assigned to the 20 mg PF-02545920 dose group in the preceding A8241021 study, will continue to receive 20 mg PF-02545920 in this study without any titration. All other subjects will be titrated to the 20 mg BID dose as follows: 5 mg BID for 7 days, 10 mg BID for 7 days, 15 mg BID for 7 days, then 20 mg BID for the remainder of the treatment phase. Titration is in place to reduce incidence of AEs, frequent monitoring is in place for neutropenia, and an option for de-escalation by 5 mg decrements (temporary or

permanent) will be available should the investigator consider the AE intolerable (see Guidance on clinical management of subjects with acute extrapyramidal symptoms, Appendix 1).

Subjects who are discontinued (Early Termination) at or after Day 14 should complete as many of the Month 12 (V8) assessments as possible. Subjects should return to complete the Follow-up visit whenever possible.

Based on the total number of 260 subjects expected to be randomized in study A8241021, up to 260 subjects may take part in this open label extension.

[figure not shown]
[figure not shown]

Figure 1. Study Design Schematic

20 mg BID PF-02545920 (up to 260 subjects)

- Titration schedule for subjects previously not assigned 20mg PF-02545920:
 - 5mg BID x 7 days
 - 10mg BID x 7 days
 - 15mg BID x 7 days
 - 20mg BID to Month 12

5mg step de-escalation option available for intolerable AE

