6.2. Adverse Events

All AEs occurring during the course of the study will be coded using the most current MedDRA coding dictionary.

All AEs (serious and non-serious) reported from the first day of study treatment through and including 28 calendar days after the last administration of the study drug will be considered treatment emergent AEs (TEAEs).

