8. STATISTICAL METHODOLOGY AND STATISTICAL ANALYSES

8.1. Statistical Methods

The Safety population will be used in the analyses of the safety data. The FAS analysis set will be utilized for efficacy endpoints.

All efficacy endpoints will be summarized descriptively at each visit for all subjects as well as separated by three groups (ie, from PF 20mg, from PF 5mg, and from Placebo). 90%CI will be provided for the mean. Plots with the mean over time with 90%CI will be generated for all subjects as well as by three different groups.

Baseline and change from baseline for each efficacy endpoints will also be summarized descriptively at each visit for all subjects as well as separated by three groups. Plots with mean change from baseline over time with 90%CI will be generated for all subjects as well as by three different groups.

Due to the unexpected termination of the study, any early termination visits (ET), which occurred on and after Dec. 16th, 2016, will not be included in the summary tables and plots. These data will be listed only.

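### Adverse event incidence, one of the primary safety endpoints, is planned only as a crude percentage although the study ended early; a secondary point is that the 28-day TEAE window runs past planned non-serious AE collection

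*Protocol*

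**What the plan says.** **AE summary.** Protocol 9.2.1 lists eight primary safety endpoints. The first is "The number and proportion of subjects with adverse events", and for the analysis "the number and percent of subjects reporting each event will be summarized". Early leavers are covered by one sentence: "Subjects who prematurely discontinued the trial will be evaluated on the basis of data collected at each visit attended". The denominator is left general: "The denominator for percentages will be based on the number of subjects appropriate for the purpose of analysis". The safety population is everyone with at least one open-label dose. SAP 8.3.5 adds only that AEs follow the sponsor's reporting standards, which are not part of the documents. SAP 8.3.1 presents safety for all subjects and by three prior-dose groups (20 mg, 5 mg, placebo).

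**Termination.** SAP 8.1 opens its last paragraph with "Due to the unexpected termination of the study" and then moves early termination visits on or after 16 December 2016 from tables and plots to listings. It changes nothing in how AEs are summarised.

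**Windows.** SAP 6.2 says that AEs, serious and non-serious, reported from first treatment "through and including 28 calendar days after the last administration of the study drug will be considered treatment emergent AEs (TEAEs"). Protocol 8.2 has AEs recorded on the CRF "from the time the subject has taken at least 1 dose of study treatment through the last subject visit", with active SAE reporting to the sponsor for 28 days after the last dose. Protocol 3 fixes the end of scheduled contact: "The final scheduled visit is a Follow-up visit 7-14 days after the last dose". After early termination, that visit takes place only where possible.

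**The concern.** The primary objective is long-term safety in a study designed to run 12 months. When follow-up is cut short, a subject with a few weeks on drug counts the same in the denominator as one with a full year. The resulting percentage estimates neither a 12-month risk nor an event rate. A reader who sets it beside the 12-month objective will take it as reassurance that part of the cohort was not followed long enough to give. The events most affected are those a long-term extension exists to find: late ones, or ones that accrue steadily.

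The TEAE window is a different and smaller matter. Planned collection of serious and non-serious events stops at different times after the last dose, so the post-dose part of a TEAE table is unevenly ascertained.

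**Working it through.** **No figure to reproduce.** The documents state no AE rate, precision, dropout or follow-up distribution for this endpoint, and 260 is an enrolment ceiling. The sizes below are illustrations under stated assumptions.

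**Inputs.**
- Assumed 12-month risk p = 10%. Protocol Appendix 1 predicts 10% or less for EPS needing management at titrated 20 mg; here the figure is only a convenient value.
- Time unit: 12 months.
- Follow-up times: assumed.
- Early-onset pattern: Protocol 1.2.2, where 5 of 6 subjects with dystonia on 15 mg in study A8241012 had it before Day 7.

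**Step 1: crude percentage under constant hazard.** λ = −ln(1 − 0.10) = 0.1054.

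| Assumed follow-up | Formula | Crude % |
|---|---|---|
| All 12 months | 1 − exp(−λ) | 10.0 |
| 30% of subjects truncated uniformly over 0–12 months, rest complete | 0.7 × 10.0 + 0.3 × 5.09 | 8.5 |
| All stop at 9 months | 1 − exp(−0.75λ) | 7.6 |
| 50% truncated uniformly, rest complete | 0.5 × 10.0 + 0.5 × 5.09 | 7.5 |
| All stop at 6 months | 1 − exp(−0.5λ) | 5.1 |
| All truncated uniformly over 0–12 months | 1 − (1 − exp(−λ))/λ = 1 − 0.1/0.1054 | 5.1 |

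For p = 20% (λ = 0.2231), uniform truncation of everyone gives 10.4%, and of 30% of subjects 17.1%. An extreme case, with everyone stopping at 3 months, takes 10% to 2.6%; nothing in the documents points to it.

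**Step 2: what an exposure-adjusted rate would return.** In the last row of the table, expected time at risk to first event is λ⁻¹ × 0.0509 = 0.483 subject-years per subject. The rate is 0.0509/0.483 = 0.1054, or 10.5 per 100 subject-years, and 1 − exp(−0.1054) = 10%. The full risk is recovered, provided termination is unrelated to a subject's AE risk.

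**Step 3: early-onset events.** Put 5/6 of the 10% risk (8.33%) in the first week. The remaining conditional risk is 1 − 0.9/0.9167 = 1.82% over 12 months, so λ = 0.0183. If all subjects stop at 9, 6 or 3 months, the crude figure is 9.6%, 9.2% or 8.8%. The understatement is about 1 point or less.

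**Step 4: the TEAE window.** The gap beyond the last scheduled visit is 28 − 14 = 14 days to 28 − 7 = 21 days, or 50% to 75% of the post-dose window. For a 12-month completer the TEAE period is 365 + 28 = 393 days, of which the gap is 14/393 = 3.6% to 21/393 = 5.3%. If the Step 1 hazard continued after dosing, risk to Day 393 is 10.7%, against 10.4% to Day 379 and 10.2% to Day 372: a difference of about 0.4 to 0.5 points.

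**The case against.** The strongest reply is that the plan never calls the percentage a 12-month risk. SAP 4.1 states that no hypothesis attaches to the primary variables, and Protocol 9.2.1 says how early leavers are handled. A proportion of subjects with events is a correct description of what was observed. That stands: the plan contains no false statement here. What it lacks is a summary that answers the long-term question once follow-up is unequal.

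Other points also stand in part.
- The sponsor's reporting standards may already require exposure tables. A reader might infer that none will be produced; the documents do not show that. They show only that the SAP does not ask for them.
- A reader might infer that AE incidence is the sole primary endpoint. It is one of eight.
- SAP 8.3.2 and 8.3.4 report disposition, and discontinuations and dose reductions due to AEs. SAP 8.3.7 lists subjects meeting the WBC/ANC criteria. These make truncation visible but do not correct a percentage for it.
- No passage shows that follow-up differs between prior-dose groups, and no between-group AE test is planned. Titration does delay 20 mg to Day 22 in two groups (21/365 = 5.8% of a full year), but that is time at full dose, not time in the study.

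On the window, two stronger readings fail. One is that the mismatch lowers the on-treatment risk; the gap falls after the last dose, so it cannot. The other is that only SAEs can appear in the gap. Protocol 6.4 keeps subjects who merely stop treatment in the study and follows those removed for safety until the causative events resolve or stabilise. Protocol 6.2.9 allows unscheduled visits at any time, and SAP Appendix 3 accepts Follow-up data to Day 385, 20 days after Day 365. Non-serious events can therefore be recorded in the gap. If the wording in Protocol 8.2 meant the last visit of the whole study, the gap would shrink for most subjects; the natural reading is each subject's own last visit.

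**Conclusion.** The point holds as an omission in analysis. A primary safety endpoint for a long-term objective is specified only as a crude percentage, and the SAP version that acknowledges termination left that unchanged. Read against 12 months, the percentage is too low for late or steady-hazard events. Under constant hazard and the truncation patterns assumed above, a 10% risk would read about 5% to 8.5%. The true size cannot be derived, because it depends on follow-up times and event timing that the documents do not give. For dystonia clustered in the first week the effect is small.

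The window mismatch is real but minor: 14 to 21 post-dose days without planned non-serious collection for subjects who make the Follow-up visit, and up to 28 for those whose last visit coincides with their last dose. Its consequence is uneven post-dose ascertainment, worth roughly half a percentage point in the illustration.

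**What to change.** 1. In SAP 8.3.5, specify duration of exposure, subject-years, and exposure-adjusted incidence per 100 subject-years (subjects with a first event over time at risk), pooled and by prior-dose group, beside the existing number and percent. State the denominator. If the sponsor standards already provide this, cite them explicitly.
2. For key AEs such as akathisia and neutropenia, add Kaplan-Meier cumulative incidence, censored at the end of each subject's AE follow-up. State the assumption that censoring by the termination is non-informative.
3. State whether the SAP 8.1 exclusion of late early termination visits applies to safety tables, since this bears on where AE follow-up ends.
4. Reconcile SAP 6.2 with Protocol 8.2 and the Follow-up visit timing. Keep every recorded event; report AEs with onset after the last scheduled visit separately, split into serious and non-serious. Do not drop non-serious events after day 14, because that would discard data from subjects followed longer.

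The cost is SAP wording and a few more table columns. The protocol already provides for dosing records and AE reporting, so no new data collection should be needed. The exposure-adjusted rate assumes a roughly constant hazard, so for early-onset events it should be read beside the crude percentage or the Kaplan-Meier curve.
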